## 8.6.2 Stopping Rules for Renal Function Test Results / Temporary Stopping Rules for Renal Function Test Results

In the event of an eGFR (by CKD-EPI formula) meeting any of the following criteria, or any change in renal biomarkers deemed by the nephrologist to require further evaluation, a serum creatinine and 24-hour urine sample for creatinine clearance and protein should be obtained:

- 1. eGFR (CKD-EPI) decrease of > 40% from Baseline
- 2. eGFR (CKD-EPI) value  $< 45 \text{ mL/min}/1.73 \text{ m}^2$

Dosing of a patient with Study Drug (ISIS 703802) will be stopped permanently if 24-hour urine testing confirms any of the following values in the absence of an alternative explanation:

- 1. Urine protein is > 1.0 g
- 2. Creatinine clearance decrease of > 40% from Baseline
- 3. Creatinine clearance  $< 45 \text{ mL/min}/1.73 \text{ m}^2$

Irrespective of whether the stopping rule is confirmed or not, the follow-up schedule and frequency of renal function monitoring after the initial event will be determined by the Study Medical Monitor in consultation with the Investigator. The Investigator should consider consulting a local nephrologist for any change of renal function that presents a concern. If a renal biopsy is performed, a sample specimen should be made available for examination by an independent renal pathologist who has been engaged by the Sponsor to review such specimens.

Dose adjustments, including dose interruptions, and/or decreasing the dose or dose frequency will be allowed for safety. Any proposed adjustments to treatment schedule must be discussed with, and approved by, the Study Medical monitor prior to initiation.

## 8.6.3 Stopping Rule for Platelet Count Results

Actions to be taken in the event of a low platelet count are summarized in Table 3 below.

In the event of any platelet count less than 50,000/mm^3, or a platelet count less than 75,000/mm^3 that occurs while the subject is already on reduced dose, dosing of the subject with Study Drug will be stopped permanently (Table 3). Platelet count will be monitored daily until 2 successive values show improvement then monitored every 2-3 days until platelet count is stable.

Administration of steroids is recommended for subjects whose platelet count is less than 25,000/mm^3. Recovery in platelet count may be accelerated by administration of high dose steroids. Treatment guidelines for immune thrombocytopenia (Provan et al. 2010) recommend Dexamethasone 40 mg daily for 4 days every 2-4 weeks for 1-4 cycles; Prednis(ol)one 0.5-2 mg/kg/d for 2-4 weeks then taper; or methylprednisolone 30 mg/kg/day for 7 days

(note: may require continuation with oral steroids after methylprednisolone).

In the event of a platelet count < 75,000/mm^3 and  $\geq$  50,000/mm^3, dosing of a subject with Study Drug should be suspended temporarily until the platelet count has recovered to  $\geq$  100,000/mm^3. If dosing is continued, it must be at a reduced dose as shown in Table 3. The suitability of the subject for continued dosing will be determined by the Investigator in consultation with the Study Medical Monitor and will be based on factors such as the original rate of decline in the subject's platelet count, whether any bleeding events were experienced by the subject, and the speed of recovery of platelet count after interruption of dosing.

If, after reintroduction of Study Drug, the platelet count again falls below 75,000/mm^3, then dosing of the subject with Study Drug will be stopped permanently.

Once a subject commences weekly monitoring, this frequency of monitoring should continue until the platelet count returns to the normal range ( $\geq 140,000/\text{mm}^3$ ) for 2 successive values.

Any unreportable platelet count result must be rechecked and determined not to have met a stopping rule before dosing can continue.

Platelet Count on Rx	Drug Dose	Monitoring
Normal range, > 140K/mm 	No action	Monitor every 14 days (+/- 2 days)
≥100K to <140K/mm 	No action	Closer observation Monitor every week *
≥75K to <100K/mm 	Permanently reduce as follows:	Closer observation
	Reduce to 10 mg every week	Monitor every week*
> 50K to <75K/mm 	Pause dosing When platelet count returns to ≥ 100K/mm  restart dosing as follows only if approved by Sponsor Medical Monitor: Reduce to 10 mg every week or Permanently discontinue Study Drug if it occurs while on already reduced dose	Closer observation Monitor every 2-3 days until 2 successive values show improvement Consider discontinuation of antiplatelet agents/non-steroidal anti-inflammatory drug (NSAIDS)/ anticoagulant medication
> 25K to <50K/mm 	Permanently discontinue Study Drug	Closer observation: Monitor daily until 2 successive values show improvement then monitor every 2-3 days until platelet count stable Discontinue antiplatelet agents/NSAIDS/anticoagulant medication while platelet count < 50K/mm  if possible. Refer to hematologist to provide diagnostic and therapeutic management.
< 25K/mm 	Permanently discontinue Study Drug	Closer observation: Monitor daily until 2 successive values show improvement then monitor every 2-3 days until platelet count stable Steroids recommended** Consider need for hospitalization t Discontinue antiplatelet agents/NSAIDS/anticoagulant medication while platelet count < 50K/mm  if possible Refer to hematologist to provide diagnostic and therapeutic management.

# Table 3 Actions in Subjects with Low Platelet Count

\* Once a subject commences weekly monitoring this frequency of monitoring should continue until the platelet count returns to the normal range (≥ 140,000/mm^3) for 2 successive values.

\*\* Recovery in platelet count may be accelerated by administration of high dose steroids. Treatment guidelines for immune thrombocytopenia (Provan et al. 2010) recommend Dexamethasone 40 mg daily for 4 days every 2-4 weeks for 1-4 cycles; Prednis(ol)one 0.5-2 mg/kg/d for 2-4 weeks then taper; or Methylprednisolone 30 mg/kg/day for 7 days (note: may require continuation with oral steroids after methylprednisolone).

## 8.7 Adjustment of Dose and/or Treatment Schedule

Dose frequency adjustments for platelet count reduction must be made in accordance with Section 8.6.3 and Table 3 (above).

Other dose adjustments, including dose interruptions, and/or decreasing the dose will be allowed for safety or tolerability in consultation with the Sponsor Medical Monitor.

Subjects may have their dose interrupted in response to AEs in consultation with Study Medical Monitor.

# 8.8 Discontinuation of Study Drug/Treatment

A subject must permanently discontinue study treatment for any of the following:

- The subject becomes pregnant. Report the pregnancy according to instructions in Section 9.5.4
- The subject withdraws consent
- The subject experiences an adverse event (AE) that necessitates permanent discontinuation of Study Drug
- The subject develops laboratory test abnormalities that meet any of the stopping rules listed in Sections 8.6.1 to 8.6.3
- When a platelet count of less than 50,000/mm^3, or a platelet count less than 75,000/mm^3 while the patient is on a reduced dose.

The reason for discontinuation of Study Drug Treatment must be recorded in the electronic Case Report Form (eCRF) and source documentation.

For subjects who discontinue treatment early every effort should be made to complete the early termination study procedures and observations at the time of withdrawal (see Appendix A). Subjects should then be entered into the post-treatment evaluation period.

If a subject discontinues treatment after only 1 dose, then the post-treatment evaluation procedures should be followed.

# 8.8.1 Follow-up Visits for Early Termination from Treatment Period or from Post-Treatment Follow-up Period

Any subject who discontinues early from the treatment period or from post-treatment follow-up period should be followed as per the platelet monitoring rules shown in, Section 8.6.3 for the first 6 weeks after discontinuing Study Drug and then at 8 and 13 weeks post end of treatment period (as per visit schedule). If the subject declines or is unable to participate in the above, the early termination visit procedures should be performed at the time of withdrawal, at a minimum, and ideally within 2 weeks from the last dose of Study Drug. In addition, the investigator should clarify what type of follow-up the subject is agreeable to: in person, by phone/mail, through family/friends, in correspondence/communication with other physicians, and/or from review of the medical records. Wherever possible these subjects should continue to be followed up via the agreed means to collect information on adverse events, concomitant medications and survival status. At the very least, the patient's status at the end of the protocol defined study period should be ascertained and documented.

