# 8.5.3 Safety Monitoring Rules for Platelet Count Results

All subjects will have platelet counts monitored every 2 weeks for the duration of the study treatment period and must not receive Study Drug without an interpretable platelet count result in the prior 2 weeks. Upon completion of study drug dosing, platelets should be monitored every 2 weeks for the first 6 weeks and then at 8 and 13 weeks post last dose (as per visit schedule).

All platelet count results must be reviewed promptly (within 48 hours of receipt) by the Investigator or the designee to ensure that the count has not met the stopping rule and to determine whether the rate of decline is suggestive that the subject could be approaching the dose interruption rule of 75,000/mm^3.

Any case of a platelet count reduction to levels below 50,000/mm^3 (Grade 3 or Grade 4) is considered an adverse event of special interest and should be reported in an expedited fashion to the Sponsor. In this case, the Investigator should refer the subject to a hematologist to provide diagnostic and therapeutic management.

Lab alerts related to platelet monitoring/stopping rules are issued when: 1) platelet counts are < 140,000 mm^3; 2) when platelet count is  $\geq$  30% decreased from Baseline, or 3) when the hematology sample is unreportable. All these lab alerts, are reviewed promptly by the Medical Monitor and instructions are communicated to the Investigator and the study personnel within 24 hours of receiving an actionable lab alert.

Actions to be taken in the event of reduced platelet count are shown in Table 3.

In the event of a platelet count  $< 100,000/\text{mm}^3$  the laboratory tests outlined in Table 3, should be performed as soon as possible. In addition to action taken as outlined in Table 3, in the event of a platelet count  $< 100,000/\text{mm}^3$ , tests outlined in Appendix F should be performed as soon as possible. Additional lab tests, if warranted, will be determined by the Sponsor Medical Monitor or designee in consultation with the Investigator.

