#### 9.5 **Procedures for Handling Special Situations**

#### 9.5.1 Abnormalities of Laboratory Tests

Clinically-significant abnormal laboratory test results may, in the opinion of the Investigator, constitute or be associated with an AE. Examples of these include abnormal laboratory results that are associated with symptoms, or require treatment (e.g., bleeding due to thrombocytopenia, tetany due to hypocalcemia, or cardiac arrhythmias due to hyperkalemia). Whenever possible, the underlying diagnosis should be listed in preference to abnormal laboratory values as AEs. Clinically-significant abnormalities will be monitored by the Investigator until the parameter returns to its baseline value or until agreement is reached between the Investigator and Sponsor Medical Monitor. Laboratory abnormalities deemed not clinically-significant (NCS) by the Investigator should not be reported as AEs. Similarly, laboratory abnormalities reported as AEs by the Investigator should not be deemed NCS on the laboratory sheet. The Investigator is responsible for reviewing and signing all laboratory reports. The signed clinical laboratory reports will serve as source documents and should include the Investigator's assessment of clinical significance of out of range/abnormal laboratory values. All platelet count results must be reviewed promptly (within 48 hours of receipt) by the Investigator or the designee to ensure that the count has not met the stopping rule and to determine whether the rate of decline is suggestive that the patient could be approaching the dose interruption rule of 75,000/mm^3 as specified in Section 8.6.3. Any case of a platelet count reduction to levels below 50,000/mm^3 (Grade 3 or Grade 4) is considered an adverse event of

special interest and should be reported in an expedited fashion to the Sponsor as per Sections 9.3.3.1 and 9.4.1).

All results of liver function tests must be reviewed promptly (within 48 hours of receipt) by the Investigator or the designee to ensure that the result has not met the stopping rules per Section 8.6.1.

All results of renal function tests must be reviewed promptly (within 48 hours of receipt) by the Investigator or the designee to ensure that the result has not met the stopping rules per Section 8.6.2.

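### After early discontinuation, Section 8.8.1 lets scheduled platelet sampling step down at week 6 whatever the count, whereas Section 8.6.3 and Table 3 end on the count

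*Combined protocol and SAP*

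**What the plan says.** All references are to the protocol as amended (Amendment 1) and its clarification letters.

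- **Section 8.8** lists the reasons for stopping drug, the platelet stopping rules among them, and continues: "Subjects should then be entered into the post-treatment evaluation period".
- **Section 8.8.1** governs platelet follow-up for anyone who discontinues early. The Section 8.6.3 rules apply "for the first 6 weeks after discontinuing Study Drug and then at 8 and 13 weeks post end of treatment period".
- **Section 8.6.3, permanent stop.** This covers any count below 50,000/mm³, or one below 75,000/mm³ "that occurs while the subject is already on reduced dose, dosing of the subject with Study Drug will be stopped permanently". Sampling then runs as follows: "Platelet count will be monitored daily until 2 successive values show improvement then monitored every 2-3 days until platelet count is stable".
- **Table 3, 50,000 to below 75,000/mm³:** "Monitor every 2-3 days until 2 successive values show improvement".
- **Table 3, the two rows from 75,000 to below 140,000/mm³:** weekly sampling, with the footnote "Once a subject commences weekly monitoring this frequency of monitoring should continue until the platelet count returns to the normal range", defined there as at least 140,000/mm³ on two successive values.
- **Section 8.5.3** and **Appendix A footnote h** (as clarified by Administrative Clarification Letter 2) also give fixed calendars ending with week 8 and week 13 counts. Neither makes them depend on the platelet value.

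**The concern.** The end points are of different kinds. Section 8.8.1 ends the Section 8.6.3 rules on a date, while Section 8.6.3 and Table 3 end on the platelet count. No text says which governs if the count is still low at week 6. A site that follows Section 8.8.1 to the letter could drop to two scheduled counts in a subject whom Table 3 would still sample weekly or more often.

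Section 8.8.1 is also the provision that applies to subjects stopped under the platelet rules. Section 2.5.2 reports no platelet changes with this drug in volunteers, mice or monkeys. It does report severe thrombocytopenia in some subjects given unconjugated oligonucleotides of the same chemical class. Amendment 1 gave continuity of monitoring in subjects with a decreased count as one reason for its platelet changes (cited for intent only). The stake is safety monitoring; the triglyceride endpoint is not involved.

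**Working it through.** The plan gives no figure of its own here, so the check compares the schedules week by week.

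**Inputs**
- The treatment period ends one dosing interval, 1 week, after last dose (Appendix A, footnote o).
- Follow-up weeks 8 and 13 therefore fall at 8 + 1 = 9 and 13 + 1 = 14 weeks after last dose.
- Letter 2 runs the 14-day sampling through 6 weeks after the treatment period, that is to week 6 + 1 = 7 after last dose.
- Assumption: discontinuation is dated at last dose, so the six-week phase ends at week 6.

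**Scheduled counts over weeks 7 to 14 after last dose, weekly-band subject**
- Section 8.8.1 alone: weeks 9 and 14, so 2 counts. The gaps are 9 − 6 = 3 and 14 − 9 = 5 weeks.
- With a week 7 count from footnote h: weeks 7, 9 and 14, so 3 counts. The gaps are 1, 2 and 5 weeks.
- Table 3 weekly rule, if 140,000/mm³ is not reached twice in succession: 14 − 7 + 1 = 8 counts.

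**Earlier recovery.** Let m be the week in which the second successive value of at least 140,000/mm³ is obtained. If Table 3 monitoring continued to m, with weeks 9 and 14 kept as a minimum, the counts are weeks 7 to m plus 9 and 14. The extra counts run from total − 3 to total − 2.

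| End condition met at week m | Total counts | Extra over current text |
|---|---|---|
| 7 | 3 | 0–1 |
| 8 or 9 | 4 | 1–2 |
| 10 | 5 | 2–3 |
| 11 | 6 | 3–4 |
| 12 | 7 | 4–5 |
| 13 or later | 8 | 5–6 |

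There is no difference if the end condition is met by week 6 or Table 3 was never triggered.

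**Sensitivity to the anchor**
- Discontinuation dated 7 days after last dose: the phase ends at week 7, and weekly sampling over weeks 8 to 14 gives 7 counts against 2, so at most 7 − 2 = 5 extra.
- Weeks 8 and 13 counted from last dose, as Section 8.5.3 words it: weekly sampling over weeks 7 to 13 gives 7 counts against 2, with gaps of 2 and 5 weeks.

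**Subjects stopped for platelets.** Their sampling is daily, then every 2–3 days, until the count is stable. The documents give neither a definition of stable nor a time to reach it, so no count can be derived. A subject still on that schedule at week 6 would differ by more than the table shows.

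**The case against.** The strongest reply is that the protocol uses fixed calendars as a floor and lets Table 3 govern low counts. Section 8.5.3 orders counts every two weeks on treatment, again without a condition on the value, yet Table 3 plainly overrides it. Nothing in Section 8.8.1 cancels Section 8.6.3 after week 6, and a site that keeps sampling to Table 3 satisfies both.

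There are also real safeguards:
- Section 8.5.3 issues a laboratory alert for any count below 140,000/mm³ or a fall of at least 30% from Baseline, with Medical Monitor review. Section 6.2 adds that the Sponsor and CRO Medical Monitors agree on the action.
- Section 8.5 requires confirmation of results meeting the monitoring criteria, ideally within 3 days, in the post-treatment period as well.
- Section 9.5.1: "Clinically-significant abnormalities will be monitored by the Investigator until the parameter returns to its baseline value or until agreement is reached" with the Medical Monitor.
- Below 50,000/mm³, Section 9.3.3.1 requires reporting as for serious events, and "the Investigator should refer the subject to a hematologist to provide diagnostic and therapeutic management".
- Section 3.4 allows extra visits at a frequency set by the Medical Monitor.

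Most of this stands, and it rules out three stronger readings that a reader might infer:
- **That low platelets would go unmonitored.** The safeguards above contradict this.
- **That a subject could go five weeks without a sample after a low week 9 result.** Five weeks is the gap between scheduled counts; a low result would call for a repeat and raise an alert.
- **That 2–3 against 8 describes subjects stopped for low platelets.** It describes the weekly band, which is not a stopping tier. Table 3 does not say that a stabilised subject then moves to weekly sampling.

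The floor reading is possible but does not settle the matter, because Section 8.8.1 itself attaches the six-week limit to Section 8.6.3. The alerts and repeats need a blood draw first, and the other provisions rest on judgement, agreement or case-by-case decisions. None restores the scheduled frequency.

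**Conclusion.** The point holds in a limited form. Section 8.8.1 sets a time limit on rules that otherwise end on the count, and the two are not expressly reconciled. Literal compliance may reduce scheduled sampling while the end condition is unmet. In the weekly band the difference over weeks 7 to 14 is at most 5–6 counts, shrinking to 0–2 if recovery is confirmed by week 9. These figures assume discontinuation is dated at last dose; the other anchors give at most 5.

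Few or no subjects may be affected. Section 3.3 plans 3 subjects, possibly 6, and Section 5.2 excludes platelets below the lower limit of normal at entry. The matter is a low-priority safety-monitoring improvement with no bearing on the primary endpoint.

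**What to change.** Add one sentence to Section 8.8.1: the week 8 and week 13 counts are a minimum, and monitoring under Section 8.6.3 and Table 3 continues past week 6 until its own end condition is met. Subjects who have met that condition, or never triggered it, move to the week 8 and week 13 counts alone.

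Put a matching cross-reference in Section 8.5.3 and Appendix A footnote h, since both carry the same unconditional calendar and would otherwise keep the ambiguity alive. This can be done by amendment or clarification letter; Letter 2 has already dealt with platelet timing.

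The burden is about 5–6 extra blood counts at most for a weekly-band subject, and more for one still sampled every 2–3 days, in each case only while the end condition is unmet.

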#### 8.9 Withdrawal of Subjects from the Study

Subjects must be withdrawn from the Study for any of the following:

- Withdrawal of consent
- The subject is unwilling or unable to comply with the protocol
- The subject meets any of the Exclusion Criteria (see Section 5.2) after enrolling in the study that in the opinion of the Investigator represents a safety risk to the subject

Other reasons for withdrawal of subjects from the Study might include:

- At the discretion of the Investigator for medical reasons
- At the discretion of the Investigator or Sponsor for noncompliance
- Significant protocol deviation

All efforts will be made to complete and report the observations as thoroughly as possible up to the date of withdrawal. All information, including the reason for withdrawal from Study, must be recorded in the eCRF.

Any subject who withdraws consent to participate in the Study will be removed from further treatment and study observation immediately upon the date of request. These subjects should be encouraged to complete the early termination study procedures and observations at the time of withdrawal (Appendix A). For subjects withdrawn for reasons other than withdrawal of consent every effort should be made to complete the early termination study procedures and observations at the time of withdrawal (see Appendix A). The Investigator should clarify what type of follow-up the subject is agreeable to: in person, by phone/mail, through family/friends, in correspondence/communication with other physicians, and/or from review of the medical records. Wherever possible these subjects should continue to be followed up via the agreed means to collect information on adverse events, concomitant medications and survival status. At the very least, the patient's status at the end of the protocol defined study period should be ascertained and documented.

#### 8.10 Concomitant Therapy and Procedures

The use of concomitant therapies or procedures defined below must be recorded on the subject's eCRF. Adverse events related to administration of these therapies or procedures must also be documented on the appropriate eCRF.

